NOTE: In case of early withdrawal from the study, early withdrawal assessments (ie, physical examination, vital signs, CD4+ cell count [as applicable], [serious] adverse events and concomitant medications review, immunogenicity, and virologic assessments) should be obtained. Subjects who wish to withdraw consent will be offered an optional visit for safety follow-up (before the formal withdrawal of consent); the subject has the right to refuse.

- Screening may be split into multiple days or visits. Retesting of values (eg, safety laboratory) that lead to exclusion is allowed only once using an unscheduled visit during the screening phase. The safety laboratory assessments at screening are to be performed within 28 days prior to the prime vaccination and may be repeated if they fall outside this time window. If rescreening is required, all screening procedures (except TOU) should be repeated (unless the TOU has been revised in the meantime, in which case it needs to be taken again) (see Section 9.1.2).
- In addition to the assessments scheduled for the 42-day post-boost visit, subjects will be instructed to contact the investigator before the next visit if they experience any adverse event or intercurrent illness that they perceive as relevant and/or can be possibly related to study vaccine in their opinion. After unblinding a part (ie, when the last subject in that part completed the 6-month post-boost visit or discontinued earlier), subjects who received placebo will be contacted by the site to communicate that they have completed the study and no further follow-up is required. However, subjects who received placebo and reach the 1-year post-boost visit (Part 1 and Part 2, Group 2: Day 380; Part 2, Group 1: Day 394) prior to unblinding will be required to attend the 1-year post-boost visit.
- Only subjects who received Ad26.ZEBOV or MVA-BN-Filo will be followed up for collection of serious adverse event and immediate reportable event information post unblinding.

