10. SUBJECT COMPLETION/DISCONTINUATION OF STUDY VACCINE/WITHDRAWAL FROM THE STUDY

10.1. Completion

A subject will be considered to have completed the study if he or she has completed all assessments at the 6-month post-boost visit for subjects who received placebo or at the 1-year post-boost visit for subjects who received Ad26.ZEBOV and MVA-BN-Filo.

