1.5. Randomization and Blinding

Both Parts 1 and 2 of the study have completed randomization. Central randomization was implemented in this study. The randomization was used to minimize bias in the assignment of subjects to vaccination schedules (groups), to increase the likelihood that known and unknown subject attributes (eg, demographic and baseline characteristics) are evenly balanced across groups, and to enhance the validity of possible comparisons across groups. In addition, randomization was used to minimize bias in the assignment of subjects to study vaccine (active vaccine versus placebo). The randomization within each group was balanced by using randomly permuted blocks. There was stratification by age group (subjects ≥ 18 to ≤ 50 years versus subjects > 50 years).

For Part 1, subjects were randomized in a 4:1 ratio to either receive MVA-BN-Filo or placebo on Day 1 followed by a second vaccination with Ad26.ZEBOV or placebo 14 days later. Randomization was done separately for healthy subjects (N=50) and HIV-infected subjects (N=25).

For Part 2, subjects were randomly enrolled in 1 of 2 groups at study entry to either receive Ad26.ZEBOV,MVA-BN-Filo at day 1 and day 29 or MVA-BN-Filo, Ad26.ZEBOV at day 1 and day 15 in a 4:1 ratio (ie, Group 1 versus Group 2). Within each group, subjects were randomized in a 4:1 ratio to receive active vaccine versus placebo. Randomization was done separately for healthy subjects (N=250) and HIV-infected subjects (N=250). The start of randomization of HIV-infected subjects in Part 2 was contingent upon acceptable safety data from HIV-infected subjects from Part 1.

For each part, study-site personnel (except for those with primary responsibility for study vaccine preparation and dispensation, and not involved in any other study-related procedure), the sponsor (except for specifically designated sponsor personnel who are independent of the study) and subjects will remain blinded to the study vaccine allocation until the last subject in that part has completed at least the 6-month post second vaccination visit or discontinued earlier and the database has been locked for that part.

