2.4. Definition of Subgroups

There are 2 parts (Part 1: USA, Part 2: Africa) in the study with each part having the healthy and HIV-infected cohort of subjects aged 18-70 years. The subgroups that will be used to summarize the data are shown in [Table 4](#). Primarily, the analysis of subject information, safety and immunogenicity analyses will be performed by part and cohort. Within each combination of part, cohort and vaccination (dose 1 and dose 2) interval, subject information, safety and immunogenicity data will be presented for active vaccines (ie, vaccine sequence and interval) versus placebo.

Secondly, Part 2 data (ie, ELISA [units/mL] and VNA [IC₅₀ titers]) will be presented by age stratum and on the pooled cohorts (ie, healthy and HIV-infected).

In addition, data from Parts 1 and 2 will be pooled (matching on cohort and vaccination schedule).

For each combination of cohort and vaccine sequence, the pooled data (subject information, ELISA [units/mL], VNA [IC₅₀ titers] and safety) will be presented for active vaccine versus placebo. The pooled immunogenicity data (ELISA [units/mL] and VNA [IC₅₀ titers]) will also be presented by age stratum (aged 18-50 years and aged 51-70 years) for active vaccine versus placebo. Furthermore, these data will be presented on the pooled cohorts (healthy and HIV-infected).

Table 4: Study Part, Cohort, Dose 1-Dose 2 Interval and Age Group Combinations and Parameters

Study Part	Dose 1-Dose 2 Interval	Cohort	Age Group	Analysis Parameters	
Part 1	14-day interval	Healthy	18-70 years	
 - Subject information - ELISA (units/mL) - VNA (IC₅₀ titers) 	
		HIV-infected			
Part 2	14-day interval	Healthy	18-70 years	
 - ELISpot - ICS - Ad26 VNA (Part 2 only) - Safety 	
		HIV-infected			
		Healthy	18-50 years		
 - ELISA (units/mL) - VNA (IC₅₀ titers)
			51-70 years		
		HIV-infected	18-50 years		
			51-70 years		
	Pooled Healthy and HIV-infected	18-70 years			
	Part 2	28-day interval	Healthy	18-70 years	
 - Subject information - ELISA (units/mL) - VNA (IC₅₀ titers) - ELISpot - ICS - Ad26 VNA (Part 2 only) - Safety
			HIV-infected		
			Healthy	18-50 years	
			51-70 years		
HIV-infected			18-50 years		
			51-70 years		
Pooled Healthy and HIV-infected	18-70 years				

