7. SAFETY

The safety and tolerability data include the following:

- AEs (unsolicited AEs) collected from signing of the informed consent form (ICF) onwards until the 42-day Post-dose 2 visit.
- Serious adverse events (SAEs) and immediate reportable events (IREs) collected from signing of the ICF onwards until the end of the study.
- Solicited local and systemic AEs (reactogenicity) collected until 7 days after each administration of study vaccine.

The safety and tolerability data will be summarized based on the full analysis set. The analysis will be based on the actual dose (ie, dose 1 and dose 2 for the first and second vaccinations,

respectively) that the subjects received. For example, if dose 2 is not administered to a subject, then that subject will not be included in the analysis of AEs in the Post-dose 2 period. Focus will be on safety signals detected during the Post-dose 1 and Post-dose 2 periods, as well as the Regimen period (ie, combined Post-dose 1 and Post-dose 2 periods).

In general, safety data will be evaluated separately for each part of the study. Within each part, the data will primarily be presented by cohort (healthy and HIV-infected) and by vaccination schedule. Secondly, the data from Parts 1 and 2 of the study will be pooled (ie, 14-day interval regimen) and presented separately for the healthy and HIV-infected cohorts. See [Table 4](#) for a schematic overview the subgroups to be considered for the safety analysis.

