7.1.3. Analysis Methods

In general, the AEs following vaccination will be summarized (ie, tables of descriptive statistics) by vaccination schedule and presented per period/phase. Similar summary tables will also be provided pooled by vaccine (dose).

Furthermore, unsolicited AEs will be summarized (showing number and percentage) by System Organ Class (SOC) and Preferred Term (PT). Solicited AEs (recorded by day) will be converted into the analysis format of unsolicited AEs (recorded by event), as detailed in Attachment 2. These solicited AEs will be summarized by class (local, systemic) and Preferred Term. For

solicited as well as unsolicited AEs, tables focusing on severity will be created. Focus will also be on the relationship (to the study vaccine) of the solicited systemic and unsolicited AEs.

The SAEs, AEs with fatal outcome, AEs leading to permanent stop of study vaccination, Grade 3 AEs and IREs will also be listed. A table summarizing all those parameters will further be created and presented per analysis period and vaccination schedule. Summary tabulations by SOC and PT for each of the category of events (ie, SAEs, AEs with fatal outcome, AEs leading to permanent stop of study vaccination, Grade 3 AEs and immediate reportable events) will also be generated on the entire reporting period. Subject narratives will be generated for these events, except Grade 3 AEs.

For the most frequent (at least 10% of subjects in any vaccination schedule) solicited local and systemic AEs, the duration and time to first onset of the events will also be summarized. If a subject experiences more than 1 occurrence of a solicited event, the maximum duration of the events will be used. The time to first onset is defined as:

$$[\textit{date of first onset} - \textit{reference date} + 1]$$

The reference date is the start date of each vaccination period (ie, Post-dose 1 or Post-dose 2). Duration and time to onset of AEs will be expressed in days.

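### Whole-period SAE, fatal-AE and IRE percentages compare unequal follow-up if a part was unblinded before all its placebo subjects reached 1 year

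*Protocol*

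**What the plan says.** SAEs and IREs to the end of the study belong to the primary safety endpoint (Protocol 9.2.1). SAP 7 repeats the collection window: "Serious adverse events (SAEs) and immediate reportable events (IREs) collected from signing of the ICF onwards until the end of the study".

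**Tables.** SAP 7.1.3 plans SOC and PT summaries for SAEs, fatal AEs, AEs stopping vaccination, Grade 3 AEs and IREs. The sentence ends: "immediate reportable events) will also be generated on the entire reporting period". SAP 2.4 fixes the comparison: "subject information, safety and immunogenicity data will be presented for active vaccines (ie, vaccine sequence and interval) versus placebo". Protocol 11.4 describes adverse-event summaries as the number and percentage of subjects with at least one occurrence. In SAP Table 3 the last phase (Post-dose 2 FU) ends, for the final analysis, at each subject's own last contact. Neither document specifies person-time rates or a common cut-off.

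**Follow-up.** Footnote c of the Time and Events Schedule, for Part 1 and again for Part 2, says: "Only subjects who received Ad26.ZEBOV or MVA-BN-Filo will be followed up for collection of serious adverse event and immediate reportable event information post unblinding". Under Protocol 10.1 a placebo subject is complete after having "completed all assessments at the 6-month post-boost visit for subjects who received placebo", and a vaccine recipient after the 1-year visit. There is one exception: placebo subjects who reach the 1-year visit while still blinded must attend it. Unblinding goes by part. SAP 1.5 keeps the blind until the last subject in the part "has completed at least the 6-month post second vaccination visit or discontinued earlier" and the database for that part is locked.

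**Per-period table.** For the same event categories, SAP 7.1.3 adds: "A table summarizing all those parameters will further be created and presented per analysis period and vaccination schedule".

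**The concern.** A percentage of subjects with an event depends on how long subjects are watched. If one arm is released at unblinding and the other continues to 1 year, equal event rates give a higher percentage in the arm watched longer, which here is vaccine. The table could then suggest a vaccine effect on SAEs, deaths or neuroinflammatory IREs that comes only from follow-up time.

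The planned output would not reveal this. A placebo subject released after the 6-month visit counts as a completer, so the disposition table in SAP 5.1 shows nothing unusual, and no summary of follow-up time by arm is planned.

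The point is limited to SAEs, fatal AEs and IREs. Non-serious Grade 3 AEs are collected only to 42 days post-boost in both arms.

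**Working it through.** **Inputs from the documents**
- 6-month visit at Day 195 (14-day schedule) or Day 209 (28-day schedule); 1-year visit at Day 380 or Day 394 (Protocol Table 2).
- Unblinding by part, after the last subject's 6-month visit and database lock (Protocol 3.1 and 5; SAP 1.5).
- Arm sizes (Protocol Table 1): active 40 + 20 + 160 + 160 + 40 + 40 = 460; placebo 10 + 5 + 40 + 40 + 10 + 10 = 115, of whom 100 are in Part 2. These match the 460 and 115 in SAP 1.4.

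**Assumptions, not in the documents**
- The same constant event rate in both arms, 1-10% per year.
- Time counted from dose 1 (Day 1).
- Uniform accrual over A days; L days from the part's last 6-month visit to unblinding.

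**1. The plan's own figures.** The plan gives no figure for this issue. Its sample-size basis reproduces: for N=460 and a true incidence of 1%, 1 - 0.99^460 = 99.0%, as in Protocol Table 4. That figure does not address unequal follow-up.

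**2. Largest possible loss of placebo follow-up.** 380 - 195 = 185 days; 394 - 209 = 185 days.

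**3. Ceiling: every placebo subject stops at the 6-month visit.** Risk = 1 - exp(-rate × days/365.25), with 379 v 194 days (14-day schedule) or 393 v 208 days (28-day schedule).

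| Rate per year | 14-day: active v placebo | Ratio | 28-day: active v placebo | Ratio |
|---|---|---|---|---|
| 1% | 1.03% v 0.53% | 1.95 | 1.07% v 0.57% | 1.88 |
| 2% | 2.05% v 1.06% | 1.94 | 2.13% v 1.13% | 1.88 |
| 5% | 5.06% v 2.62% | 1.93 | 5.24% v 2.81% | 1.87 |
| 10% | 9.86% v 5.17% | 1.91 | 10.20% v 5.54% | 1.84 |

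**4. Staggered accrual (14-day schedule, 2% per year).** A placebo subject enrolled t days before the last subject in the part loses max(0, 185 - t - L) days. Averaged over t from 0 to A, this is 185 - L - A/2 when A ≤ 185 - L, and (185 - L)²/(2A) otherwise.

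| A (days) | L (days) | Mean loss (days) | Ratio |
|---|---|---|---|
| 180 | 0 | 185 - 90 = 95 | 1.33 |
| 365 | 0 | 185²/730 = 47 | 1.14 |
| 180 | 60 | 125²/360 = 43 | 1.13 |
| 365 | 60 | 125²/730 = 21 | 1.06 |
| any | 185 or more | 0 | 1.00 |

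The ratios are close to 379/(379 - mean loss); for example 379/284 = 1.33.

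**5. What the per-period table covers.** Under SAP Table 3 the Post-dose 1 and Post-dose 2 periods end no later than relative Day 29 after each dose, by the same rule in both arms. Events after that fall in the follow-up phases, and the last of these ends at the subject's own last contact. So no planned table gives an equal-window comparison from Day 29 post-dose 2 onward.

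**The case against.** The strongest reply is that the imbalance may not have occurred. Placebo subjects who reach 1 year before unblinding must attend that visit. Protocol 3.1 expects some Part 1 subjects to reach Day 380 while still blinded. The Amendment 5 rationale says unblinding has been delayed. SAP 1 says follow-up is completed in both parts, and SAP 1.5 still writes of the blind in the future tense. If the blind held until follow-up ended, the arms have equal follow-up. This stands as a reason to expect a small effect. It does not settle the matter. No unblinding date is given, and the Day 380 remark concerns Part 1 only, whereas Part 2 holds 100 of the 115 placebo subjects. Completed follow-up is equally true if placebo subjects were released early.

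A second reply is that the study is descriptive, focuses on the post-dose periods, lists these events individually and provides narratives. The post-dose windows are indeed equal. But a descriptive study conveys safety through side-by-side percentages, and Protocol 3.2 includes placebo recipients for safety analyses. That section also describes the placebo control as running to 6 months post-boost, a point that the whole-period tables can pass.

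A reader might infer that the percentages are biased by a factor of nearly 2, or that a vaccine signal could be hidden. The documents support neither. The factor needs every placebo subject to stop at the 6-month visit, yet a part unblinds only after its last subject's 6-month visit plus lock, so earlier enrolees are followed longer. Shorter placebo follow-up raises the vaccine percentage relative to placebo; it does not mask an excess on vaccine.

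**Conclusion.** The point holds conditionally and merits a change to the SAP. If either part was unblinded before all its placebo subjects reached 1 year, the whole-period SAE, fatal-AE and IRE percentages for that part compare unequal follow-up and are biased against vaccine.

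Under equal constant rates, the expected ratio is 1.00 if unblinding came at or after every placebo subject's 1-year visit. It has a ceiling of 1.84 to 1.95 at 1-10% per year. It is about 1.06 to 1.33 for the assumed accrual of 180 to 365 days and lock lag of 0 to 60 days at 2% per year. The rates, accrual and lag are assumptions.

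In absolute terms the numbers are small. At 2% per year on the 14-day figures, 115 placebo subjects would yield 115 × 2.05% = 2.4 subjects with an event over the full year, and 115 × 1.06% = 1.2 at the ceiling. For rare events such as IREs, though, a reader may give weight to a difference of one or two subjects.

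**What to change.** In SAP 7.1.3:

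(a) Report follow-up time by arm within part, cohort and schedule.

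(b) In the active-versus-placebo SAE, fatal-AE and IRE tables, count only events with onset up to the unblinding date of that part, or the subject's last contact if earlier. Randomisation then makes the windows comparable.

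(c) For the full period, give exposure-adjusted rates: subjects with an event per 100 person-years, with exact confidence intervals. These assume a roughly constant rate over time, so (b) should carry the comparison.

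(d) List or tabulate any post-unblinding events for active subjects only.

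A cut at the 6-month visit would be worse. Unblinding cannot precede a continuing subject's 6-month visit, so that cut would discard blinded, placebo-controlled data collected between that visit and unblinding.

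The cost is SAP wording and one extra set of tables from dates already held. If no placebo subject was released early, the results do not change, and (a) documents that.

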1. INTRODUCTION

Janssen Vaccines & Prevention B.V. (formerly known as Crucell Holland B.V., hereafter referred to as the sponsor), in collaboration with Bavarian Nordic (BN), and in conjunction with Walter Reed Army Institute of Research (WRAIR), is investigating the potential of a prophylactic Ebola vaccine regimen comprised of the following 2 candidate Ebola vaccines:

Ad26.ZEBOV is a monovalent vaccine expressing the full length Ebola virus (EBOV, formerly known as *Zaire ebolavirus*) Mayinga glycoprotein (GP), and is produced in the human cell line PER.C6[®].

MVA-mBN226B, further referred to as Modified Vaccinia Ankara (MVA)-BN[®]-Filo, is a multivalent vaccine expressing the Sudan virus (SUDV) GP, the EBOV GP, the Marburg virus (MARV) Musoke GP, and the Tai Forest virus (TAFV, formerly known as *Côte d'Ivoire ebolavirus*) nucleoprotein (NP), and is produced in chicken embryo fibroblast cells. The EBOV GP expressed by MVA-BN-Filo has 100% homology to the one expressed by Ad26.ZEBOV.

For the most up-to-date nonclinical and clinical information regarding Ad26.ZEBOV and MVA-BN-Filo, refer to the latest versions of the Investigator's Brochures and Addenda (if applicable).^{11,12} A brief summary of the nonclinical and clinical information is provided below.

The term "sponsor" used throughout this document refers to the entities listed in the Contact Information page(s), which will be provided as a separate document.

1.1. Background

Ebola viruses belong to the Filoviridae family and cause Ebola virus disease, which can induce severe hemorrhagic fever in humans and nonhuman primates (NHPs). Case fatality rates in Ebola disease range from 25% to 90% (average: 50%), according to the World Health Organization (WHO).²² These viruses are highly prioritized by the United States (US) Government, who has defined them as 'Category A' agents, due to the high mortality rate of infected individuals and the potential use as a bioweapon.

Currently, no licensed vaccine, treatment or cure exists for this disease.

Filoviruses are named for their long, filamentous shape. Within this filamentous virus, a single 19-kilobase (kb) negative-sense ribonucleic acid (RNA) genome encodes 7 proteins: the GP, the polymerase, the NP, the secondary matrix protein, the transcriptional activator, the polymerase cofactor, and the matrix protein. The virion surface is covered by homotrimers of the viral GP, which is believed to be the sole host attachment factor for filoviruses. Following cell entry, the viruses replicate their genomes and viral proteins in the cytoplasm using an RNA-dependent RNA polymerase, which is carried into the cell together with the virus.⁹

Nonclinical Studies

Immunogenicity and Efficacy

Immunogenicity and efficacy of the vaccine combination Ad26.ZEBOV and MVA-BN-Filo was evaluated in an NHP model (ie, *Cynomolgus macaques*, *Macaca fascicularis*). The combination was assessed in a multivalent filovirus setting in a small number (2 per regimen) of animals and the study included heterologous prime-boost regimens of adenovirus serotype 26 (Ad26), Ad35 and MVA-BN-Filo vectors expressing different Ebola and Marburg proteins. Full protection from Ebola virus disease and death after wild-type EBOV Kikwit 1995 challenge was obtained with all heterologous regimens, including the Ad26 and MVA vaccine regimen. All heterologous prime-boost regimens induced comparable immune responses against the EBOV Mayinga GP. Independently of the vaccine regimen, a strong boost effect was seen after heterologous prime-boost immunization. Two additional studies involving more animals are ongoing, to strengthen the robustness of the nonclinical efficacy data, and also to optimize the prime-boost schedule so as to obtain induction of protective immunity as quickly as possible, to specifically respond to the Ebola virus disease outbreak in West Africa.

Toxicology

A repeated-dose toxicity study in rabbits was performed with prime-boost combinations of Ad26.ZEBOV and MVA-BN-Filo. The different dose regimens were well tolerated when administered twice by intramuscular (IM) injection to New Zealand White rabbits with a 14-day interval period. Additionally, the objective was to assess the persistence, reversibility or delayed onset of any effects after a 14-day treatment-free period. In the heterologous prime-boost regimen, either vector or both were used to prime a filovirus-specific immune response and the other/same vector or both were used to boost the immune response 2 weeks later. All vaccine dosing regimens resulted in detectable EBOV GP-specific antibody titers. No significant toxicological effects (no adverse effects) were observed. The immune response was associated with transient increases in fibrinogen, C-reactive protein, globulin, decreases in hematocrit and hemoglobin, and microscopic findings in draining iliac lymph nodes, spleen and at the injection sites. The findings were noted to be recovering over a 2-week treatment-free period and were considered to reflect a physiological response associated with vaccination. There were no effects noted that were considered to be adverse.

Biodistribution

Single-dose biodistribution studies in rabbits were performed using the MVA-BN vector or the Ad26 vector in combination with another insert (Ad26.ENVA.01: an experimental, prophylactic Ad26 vector expressing the human immunodeficiency virus [HIV] type 1, Clade A envelope protein). MVA-BN distributed to the skin, muscle, blood, spleen, lung, liver, and pooled lymph nodes and was rapidly cleared (within 48 hours following vaccination). Ad26.ENVA.01 was primarily localized in the injection site muscle, the regional lymph nodes and the spleen. Three months after the single IM injection of Ad26.ENVA.01, the vaccine was cleared from most of the examined tissues. As biodistribution is dependent on the vector platform (MVA or Ad26) and not on the insert, it can be assumed that recombinant MVA-BN-Filo or Ad26.ZEBOV is distributed in the same way as the MVA-BN vector or Ad26.ENVA.01 vector, respectively.

Clinical Studies

To date, no clinical studies have been completed with Ad26.ZEBOV or MVA-BN-Filo. However, 4 Phase 1 studies (VAC52150EBL1001, VAC52150EBL1002, VAC52150EBL1003 and VAC52150EBL1004), 2 Phase 2 studies (VAC52150EBL2001 and VAC52150EBL2002) and 1 Phase 3 study (VAC52150EBL3001) are ongoing where monovalent Ad26.ZEBOV vaccine and multivalent MVA-BN-Filo vaccine are combined in homologous or heterologous prime-boost regimens in which each vector is used to prime a filovirus-specific immune response followed by a boost immunization with the same or the other vector 2 to 12 weeks later. Most subjects in the 4 Phase 1 studies have been vaccinated and are in follow-up. Two additional Phase 1 studies investigating MVA-BN-Filo are also ongoing (EBL01 and CVD-Mali Ebola Vaccine #1000). Refer to the latest versions of the Ad26.ZEBOV and MVA-BN-Filo Investigator's Brochures and Addenda (if applicable) for more details.^{11,12}

Limited data from the ongoing Phase 1 studies with Ad26.ZEBOV and MVA-BN-Filo are available.

VAC52150EBL1001, a first-in-human study, is a randomized, placebo-controlled, observer-blind study in healthy adults evaluating the safety, tolerability and immunogenicity of 4 regimens using MVA-BN-Filo at a dose of 1×10^8 50% tissue culture infective dose (TCID₅₀) and Ad26.ZEBOV at a dose of 5×10^{10} viral particles (vp): 2 regimens with MVA-BN-Filo as prime and Ad26.ZEBOV as boost at a 28- or 56-day interval, and 2 regimens with Ad26.ZEBOV as prime and MVA-BN-Filo as boost at a 28- or 56-day interval. A fifth regimen, with Ad26.ZEBOV at a dose of 5×10^{10} vp as prime, and MVA-BN-Filo at a dose of 1×10^8 TCID₅₀ at a 14-day interval was evaluated in the open-label, uncontrolled, substudy in healthy adults. VAC52150EBL1001 has enrolled 87 subjects for which 7-day post-prime safety data, blinded on a treatment group level, on 72 subjects (36 per treatment group) are available. Most of the adverse events reported were grade 1 or grade 2 in severity. Local injection site reactions were reported in 18 (50%) MVA/placebo subjects (all grade 1) and 28 (78%) Ad26/placebo subjects (grade 1 [22], grade 2 [5], grade 3 [1]). The most frequent local reaction was injection site pain, in 17 (47%) MVA/placebo subjects and 28 (78%) Ad26/placebo subjects, with 1 grade 3 case occurring in the Ad26/placebo group. Solicited systemic reactions were reported in 25 (69%) MVA/placebo subjects (grade 1 [24] and grade 2 [1]) and 31 (86%) Ad26/placebo subjects (grade 1 [22], grade 2 [7], grade 3 [1], unknown [1]). The most frequent systemic reactions were fatigue (50% overall), followed by headache (46%) and myalgia (35%). One Ad26/placebo subject experienced 3 grade 3 solicited systemic reactions (headache, myalgia and nausea). None of the subjects reported fever; however, 2 subjects had 1 temperature measurement missing. The most frequent unsolicited adverse events were decreased neutrophils, in 3 (8%) MVA/placebo subjects and 6 (17%) Ad26/placebo subjects, followed by activated partial thromboplastin time prolongation and hypokalemia, in 3 (8%) MVA/placebo subjects and 5 (14%) Ad26/placebo subjects each. Two subjects in the open-label substudy who experienced grade 3 neutropenia did not receive the boost vaccination due to contraindications to the boost (as specified in the protocol), but continued scheduled assessments as planned. All of these events were transient in nature and resolved without intervention. No deaths or serious adverse events related to the vaccine were reported during the blinded portion of the study.

VAC52150EBL1002 is a randomized, placebo-controlled, observer-blind study in healthy adults evaluating the safety, tolerability and immunogenicity of heterologous and homologous prime-boost regimens using MVA-BN-Filo and Ad26.ZEBOV administered in different doses, sequences and schedules: MVA-BN-Filo (1×10^8 TCID₅₀) as prime followed by a Ad26.ZEBOV (5×10^{10} vp) as boost at 14, 28, or 56 days after prime; Ad26.ZEBOV (5×10^{10} vp) as prime followed by MVA-BN-Filo (1×10^8 TCID₅₀) as boost at 28 days after prime; Ad26.ZEBOV (5×10^{10} vp) as prime followed by a high dose of MVA-BN-Filo (4.4×10^8 TCID₅₀) as boost at 14 days after the prime; a high dose of Ad26.ZEBOV (1×10^{11} vp) as prime followed by a high dose of MVA-BN-Filo (4.4×10^8 TCID₅₀) as boost at 28 days after the prime. VAC52150EBL1002 completed enrollment of 92 subjects; the blinded phase of the study is ongoing. No serious adverse events related to study vaccine have been reported and no safety issues have been identified to date.

VAC52150EBL1003 and VAC52150EBL1004 are randomized, placebo-controlled, observer-blind studies in healthy adults evaluating the safety, tolerability and immunogenicity of 4 regimens using MVA-BN-Filo at a dose of 1×10^8 TCID₅₀ and Ad26.ZEBOV at a dose of 5×10^{10} vp: 2 regimens had MVA-BN-Filo as prime and Ad26.ZEBOV as boost at a 28- or 56-day interval, and 2 regimens had Ad26.ZEBOV as prime and MVA-BN-Filo as boost at a 28- or 56-day interval. The blinded phase of studies VAC52150EBL1003 and 1004 are ongoing with enrollment complete in 1003. The blinded safety profile is similar to that reported in VAC52150EBL1001 and 1002 studies with so far, fewer reports of solicited local and systemic adverse events. No vaccine-related serious adverse events have been reported in either study.

Safety data generated with the 2 vectors containing different inserts are provided below:

Safety Profile of Ad26.ZEBOV

Ad26.ZEBOV is a monovalent recombinant, replication-incompetent Ad26-based vector. Only limited clinical data are available for Ad26.ZEBOV. However, adenovirus vaccine programs with other gene inserts revealed no significant safety issues. The data described below are based on the evaluation of the prototype vaccine Ad26.ENVA.01, which expresses the HIV envelope gene.¹³

Three randomized, placebo-controlled, Phase 1 studies (IPCAVD-001, IPCAVD-003, IPCAVD-004) have evaluated the safety and immunogenicity of the prototype vaccine Ad26.ENVA.01. This prototype vaccine has been administered to more than 200 healthy, HIV-negative subjects between the ages of 18 and 50 years in the US and Africa.^{13,14,15}

- In the dose-escalation study IPCAVD-001 (n=60), 2 or 3 IM doses of Ad26.ENVA.01 (1×10^9 , 1×10^{10} , 5×10^{10} , 1×10^{11} vp) were given to Ad26 seronegative subjects. There were no deaths or vaccine-related serious adverse events. Ad26.ENVA.01 was generally well tolerated at all 4 dose levels with minimal reactogenicity observed in the 1×10^9 and 1×10^{10} vp dose groups. Moderate to severe malaise, myalgia, fatigue and chills occurred in the majority of subjects 12 to 18 hours after the first dose of 1×10^{11} vp, but were resolved within 24 to 36 hours and were not seen after the second injection at this dose level. Two subjects in the 1×10^{11} vp dose group chose not to have the second injection, however, 1 of them decided to have the 6-month injection. Envelope-specific humoral and cell-mediated immune responses were induced at all 4 dose levels of vaccine.^{2,4}
- In the single-dose study IPCAVD-003 (n=24), an IM dose of Ad26.ENVA.01 (5×10^{10} vp) or placebo was given to subjects, who were stratified according to baseline Ad26 immune status, to evaluate the safety, mucosal immunogenicity and innate immune responses. Local reactogenicity comprised moderate injection site pain/tenderness and/or moderate to severe erythema which resolved within 3 days of vaccination. Transient systemic reactogenicity comprised headache, chills, joint pain, myalgia, malaise/fatigue, and fever. No deaths or vaccine-related serious adverse events were observed. Vaccination elicited both systemic and mucosal envelope-specific humoral and cellular immune responses. No increased activated total or vector-specific mucosal CD4+ T-lymphocytes following vaccination were detected in the colorectal mucosa, indicating that vaccination with Ad26 did not increase mucosal inflammation.¹
- In study IPCAVD-004 (n=217), the safety and immunogenicity of IM doses of Ad26.ENVA.01 and Ad35.ENV (an Ad35 vector expressing an HIV envelope GP used in that study at a dose of 5×10^{10} vp), given in heterologous and homologous prime-boost regimens at 3- versus 6-month intervals, was evaluated. There were 452 adverse events reported by 84 of 176 Ad26-vaccine recipients (47.7%), the majority being mild (75.5%) in severity. The proportion of subjects with moderate or severe symptoms was not statistically significantly different between vaccine and placebo. There were 3 serious adverse events: 2 serious adverse events in placebo recipients (grade 3 peritonsillar abscess and grade 4 migraine headache, both resolved with no residual effects) and 1 serious adverse event in an Ad35/Ad26 vaccine recipient (grade 4 acute myelogenous leukemia, resolved with sequelae). No deaths or vaccine-related serious adverse events were reported. Overall, 97% to 100% of subjects developed anti-envelope binding antibodies (enzyme-linked immunosorbent assay [ELISA]) after a second dose, with heterologous and homologous regimens being comparable. Immune responses in groups who received 3- and 6-month schedules were comparable. Four weeks post-vaccination, interferon (IFN)- γ enzyme-linked immunosorbent assay (ELISpot) assay showed response rates between 44% and 100%. The heterologous and homologous regimens were comparable. There was induction of Ad26-neutralizing antibodies in the majority of vaccine recipients after 2 immunizations with Ad26.ENVA.01.¹⁶

In addition, the sponsor performed a Phase 1/2a double-blind, randomized, placebo-controlled, dose-escalation study (MAL-V-A001) to evaluate the safety, tolerability and immunogenicity of 2 dose levels (1×10^{10} and 5×10^{10} vp) of Ad35.CS.01/Ad26.CS.01 (both expressing the malaria *Plasmodium falciparum* circumsporozoite antigen) prime-boost regimens in healthy subjects. The dose-escalation phase was followed by an evaluation of efficacy of the higher dose level in an experimental malaria challenge. A total of 42 subjects were enrolled and were vaccinated. The

analysis of adverse events did not show any consistent pattern suggestive of an association of Ad35.CS.01 or Ad26.CS.01 with specific adverse events. There were no serious adverse events reported during the study. No subject discontinued during a study phase (vaccination or challenge) due to adverse events. One subject in the high-dose group completed the vaccination phase and the final safety follow-up visit but did not take part in any challenge phase activities because of ongoing dyspnea. The most common related adverse events after each vaccination were injection site pain, malaise, headache, myalgia and chills. The incidence of vaccine-related adverse events was generally higher in the high-dose group than in the low-dose group. In general, incidence of malaise, headache, and myalgia were higher after the third dose (Ad26) than after the first or second doses (Ad35). Injection site pain was more commonly reported in the low and high-dose groups than by placebo subjects. There were no clinically significant changes in laboratory test parameters or vital signs data.⁵

Based on the previous clinical experience of Ad26 vector with different inserts, there has been no impact of Ad26 seropositivity on subjects' safety and only limited impact on immunogenicity results. Therefore, there are no safety concerns with regard to the inclusion of Ad26 seropositive subjects in the study, and the study subjects will not be screened for Ad26 seropositivity as part of the study eligibility criteria. The purpose of the Ad26 seropositivity assessment at baseline is to evaluate its impact, if any, on vaccine immunogenicity.

Safety Profile of MVA-BN

MVA-BN is a further attenuated version of the MVA virus, which in itself is a highly attenuated strain of the poxvirus Chorioallantois Vaccinia Virus Ankara. MVA-BN induces strong cellular activity as well as a humoral (antibody) immune response and has demonstrated an ability to stimulate a response even in individuals with pre-existing immunity against Vaccinia. One of the advantages of MVA-BN is the virus' inability to replicate in a vaccinated individual. The replication cycle is blocked at a very late stage, which ensures that new viruses are not generated and released. This means that the virus cannot spread in the vaccinated person and none of the serious side effects normally associated with replicating Vaccinia viruses have been seen with MVA-BN.

